1.1 Title

CArdiovascular safety and Renal Microvascular outcomE study with LINagliptin ([CARMELINA](#) trial)

1.2 Intended aim(s)

The primary hypothesis was that treatment with linagliptin would be non-inferior with a hazard ratio of < 1.3 compared with placebo as assessed by the time to first occurrence of any of the 3P-MACE (primary endpoint) events.

1.3 Primary endpoint for replication and RCT finding

First occurrence of CV death, non-fatal myocardial infarction, or non-fatal stroke.

1.4 Required power for primary endpoint and noninferiority margin (if applicable)

Power- 0.90. Assuming a HR of 1.0, to demonstrate non-inferiority of linagliptin versus placebo within the pre-specified non-inferiority margin of 1.3 at a one-sided α -level of 2.5%.

1.5 Primary trial estimate targeted for replication

HR = 1.02 (95% CI 0.89-1.17) comparing linagliptin to placebo (Rosenstock et al.)

2. Person responsible for implementation of replication in Aetion

[name]. implemented the study design in the Aetion Evidence Platform. S/he is not responsible for the validity of the design and analytic choices. All implementation steps are recorded and the implementation history is archived in the platform.

[figure not shown]
3. Data Source(s)

United/Optum, MarketScan, Medicare

4. Study Design Diagram

The study design diagram visualizes key aspects of the longitudinal study design for expedited review.

Design Diagram – CARMELINA TRIAL REPLICATION

5. Cohort Identification

5.1 Cohort Summary

This study will involve a new user, parallel group, cohort study design comparing linagliptin to the 2nd generation sulfonylurea (SU) antidiabetic class as a proxy for placebo. 2nd generation SUs are not known to have an impact on the outcome of interest. In addition, SUs were the most frequent background treatment in CARMELINA (after metformin), and DPP4i and SUs are preferentially prescribed to similarly older patients in real world (Paterno et al., 2019). The patients will be required to have continuous enrollment during the baseline period of 180 days before initiation of linagliptin or a comparator drug (cohort entry date). Follow-up for the outcome (3P-MACE), begins the day after drug initiation. As in the trial, patients are allowed to take other antidiabetic medications during study follow-up.

5.2 Important steps for cohort formation

5.2.1 Eligible cohort entry dates

Market availability of linagliptin in the U.S. started on May 2, 2011.

- For Marketscan: May 2, 2011-Dec 31, 2017 (end of data availability).
- For Medicare: Jan 1, 2012-Dec 31, 2017 (start- end of data availability).
- For Optum: May 2, 2011-March 31, 2019 (end of data availability).

5.2.2 Specify inclusion/exclusion criteria for cohort entry and define the index date

Inclusion and exclusion criteria were adapted from the trial as closely as possible. Definitions for all inclusion/exclusion are provided in **Appendix A** and are summarized in the flowcharts below.

5.3 Flowchart of the study cohort assembly

	Optum		Marketscan		Medicare*	
	Less Excluded Patients	Remaining Patients	Less Excluded Patients	Remaining Patients	Less Excluded Patients	Remaining Patients

All patients in the database		74,864,884		191,990,035		23,466,175
Patients who used exposure or a reference between 02 May 2011 to Dec 2017 (for Marketscan)/March 2019 (for Optum) and 01 January 2012-December 2017 for Medicare	-73,493,670	1,371,214	-190,287,730	1,702,305	-19,944,169	3,522,006
Patients who have continuous 6 months registration in the database	-185,581	1,185,633	-171,524	1,530,781	-972,275	2,549,731
Patients without prior use of reference	-877,495	308,138	-1,180,188	350,593	-1,838,491	711,240
Patients without prior use of exposure	-68,637	239,501	-59,423	291,170	-133,733	577,507
Excluded because patient qualified in >1 exposure category	-275	239,226	-211	290,959	-370	577,137
Patients who did not have missing age information	-12	239,214	0	290,959	0	577,137
Patients who did not have missing gender information	-19	239,195	0	290,959	0	577,137
Excluded based on Inclusion 1- DM Type 2	-18,341	220,854	-37,618	253,341	-10,507	566,630
Excluded based on Inclusion 5- Age >= 18	-19	220,835	-76	253,265	0	566,630
Excluded based on Inclusion 6- Body Mass Index (BMI) <= 45 kg/m2 at visit 1 (as a proxy, excluding patients with morbid obesity)	-9,096	211,739	-8,032	245,233	-13,155	553,475
Excluded based on Inclusion 8 - High risk of CV events	-64,122	147,617	-98,434	146,799	-67,114	486,361
Excluded based on Exclusion 1- Type 1 DM with ICD10 CODES	-2,983	144,634	-3,481	143,318	-12,175	474,186
Excluded based on Exclusion 2- Treatment (≥ 7 days) with GLP-1 RA, other DPP-4i or SGLT-2i	-7,712	136,922	-9,388	133,930	-23,347	450,839
Excluded based on Exclusion 3- Liver disease	-2,648	134,274	-1,931	131,999	-8,953	441,886
Excluded based on Exclusion 4- CKD Stage 5 (proxy for eGFR <15 ml/min/1.73 m2)/Dialysis	-707	133,567	-470	131,529	-3,368	438,518
Excluded based on Exclusion 5- Any history of or planned bariatric surgery	0	133,567	0	131,529	0	438,518
Excluded based on Exclusion 6- Previous cardiac procedure (CABG or PTCA or Stent) ≤ 2 months	-436	133,131	-569	130,960	-1101	437,417
Excluded based on Exclusion 8- Alcohol abuse/Drug abuse and Exclusion 10- Pregnancy	-1047	132,081	-501	130,459	-2,267	435,149
Excluded based on Exclusion 11 part 1- life expectancy less than 5 years [using combined comorbidity index as a proxy (365 days)]	-2,263	129,818	-1,125	129,334	-12,200	422,949
Excluded based on Exclusion 11 part 2- History of Malignant Neoplasm (within last 3 years)	-4,153	125,665	-4,128	125,206	-14,241	408,708
Excluded based on Exclusion 12- ACS/unstable angina (≤ 2 months prior)	-374	125,291	-332	124,874	-788	407,920
Excluded based on Exclusion 13- Stroke or TIA (≤ 3 months prior)	-2,292	122,999	-1,981	122,893	-7,081	400,839
Final cohort		122,999		122,893		400,839

* Medicare database includes only patients ≥ 65 years of age with at least one diagnosis for diabetes, heart failure, or stroke.

** Exclusion 8 and Exclusion 10 collapsed for adherence to CMS suppression guidelines.

6. Variables

6.1 Exposure-related variables:

Study drug:

The study exposure of interest is initiation of linagliptin. Initiation will be defined by no use of linagliptin or a comparator in the prior 6 months before treatment initiation (washout period).

Comparator agents:

- Initiators of linagliptin will be compared to initiators of-
 - 2nd generation sulfonylureas

Because linagliptin and comparators are frequently used as second or third line treatments of T2DM, we expect it to be unlikely that linagliptin and comparators are initiated in patients with substantially different baseline risk for proposed outcomes.

6.2 Preliminary covariates:

- Age
- Sex
- Combined Comorbidity Index (CCI), measured over the baseline covariate assessment period, defined as 180 days prior to and including index date

Covariates listed above represent only a small subset of covariates that will ultimately be controlled for in the design and analysis. We use the covariates above only for initial feasibility analyses to judge whether there is likely to be sufficient overlap between treatment groups to proceed with the study. Remaining covariates are defined only after the study has passed the initial feasibility analysis and the initial power assessment and are listed in Table 1 (**Appendix B**). These covariates are based on those used by Patorno et al. (2019).

6.3 Outcome variables and study follow-up:

6.3.1 Outcome variables

Effectiveness outcomes of interest (definitions provided in **Appendix A**):

- **Primary outcome:** 3-point major adverse cardiovascular events (MACE), i.e., non-fatal myocardial infarction, non-fatal stroke, or CV mortality
- Secondary outcomes: Individual MACE components:
 - Hospital admission for MI (for purposes of this individual component, fatal MI is included)
 - Hospital admission for stroke (for purposes of this individual component, fatal stroke is included)
 - All-cause mortality/CV mortality:
 - All-cause inpatient mortality identified using discharge status codes will be used as a proxy for “CV mortality” in commercial databases
 - Information on CV mortality through data linkage with the National Death Index (NDI) will only become available at a later date for Medicare and will be used in secondary analyses.

Control outcomes of interest (control outcomes only serve to assess aspects of study validity but are not further interpreted):

1. End Stage Renal Disease (we expect to see no association; Rosenstock et al., 2019)

Control outcome definitions

Outcome	Definition	Comments
Control Outcomes		
End Stage Renal Disease (ESRD)	
ESRD with dialysis, defined as:
 
An ICD9 diagnosis (inpatient or outpatient) for ESRD:
 
 ○ 585.5x, Chronic kidney disease, Stage V (for ESRD with no mention of dialysis) ○ 585.6x, End stage renal disease (for ESRD with dialysis) 
AND an ICD9 procedural codes for dialysis (=index date):
 
 ○ 39.95, Hemodialysis ○ 54.98, Peritoneal dialysis 
AND an additional procedural code for dialysis or physician provider code indicating dialysis procedure or ESRD-related activity within two time windows 31-60 and 61-90 days from index date. For patients who die prior to 61 days (31 days), the second (second and first) confirmation requirement(s) can be dropped. This ensures the inclusion of patients with true ESRD outcomes who die early (high early mortality) as well as early withdrawals from dialysis (which lead to high fatality within days or weeks).
	
Note- The corresponding ICD-10 codes will be used also

	
Additional procedural codes for dialysis or physician provider codes indicating dialysis procedure or ESRD-related activity include:
 
 - ICD9 procedural codes: 
 o 39.95, Hemodialysis o 54.98, Peritoneal dialysis - ICD9 diagnostic codes: 
 o 585.6x, End stage renal disease (for ESRD with dialysis) o V56.0x, encounter for dialysis NOS o V56.8x, encounter for peritoneal dialysis - CPT4 codes: 
 o 90957, 90960, ESRD related services monthly, for patients 12-19 and 20 years of age and older; with 4 or more face-to-face physician visits per month o 90958, 90961, ESRD related services monthly, for patients 12-19 and 20 years of age and older; with 2-3 face-to-face physician visits per month o 90959, 90962, ESRD related services monthly, for patients 12-19 and 20 years of age and older; with 1 face-to-face physician visit per month o 90920, 90921, ESRD related services per full month; for patients 12-19 and twenty years of age and over o 90924, 90925, ESRD related services (less than full month), per day; for patients 12-19 and twenty years of age and over o 90935, Hemodialysis procedure with single physician evaluation o 90937, Hemodialysis procedure requiring repeated evaluation(s) with or without substantial revision of dialysis prescription o 90945, Dialysis procedure other than hemodialysis (eg, peritoneal dialysis, hemofiltration, or other continuous renal replacement therapies), with single physician evaluation o 90947, Dialysis procedure other than hemodialysis (eg, peritoneal dialysis, hemofiltration, or other continuous renal replacement therapies) requiring repeated physician evaluations, with or without substantial revision of dialysis prescription o 90965, 90966, ESRD related services for home dialysis per full month, for patients 12-19 and 20 years of age and older o 90969, 90970, ESRD related services for dialysis less than a full month of service, per day; for patients 12-19 and 20 years of age and older o 90989, Dialysis training, patient, including helper where applicable, any mode, completed course o 90993, Dialysis training, patient, including helper where applicable, any mode, course not completed, per training session o 90999, Unlisted dialysis procedure, inpatient or outpatient o 99512, Home visit for hemodialysis - HCPCS codes: 
 o G0257, Unscheduled or emergency dialysis treatment for ESRD patient in a hospital outpatient dept. that is not certified as an ESRD facility o G0314, G0317, ESRD related services during the course of treatment, for patients 12-19 and 20 yrs of age and over to include monitoring for the adequacy of nutrition, etc. w/4 or more physician visit per month o G0315, G0318, ESRD related services during the course of treatment, for patients 12-19 and 20 yrs of age and over to include monitoring for the adequacy of nutrition, etc. w/2 or 3 physician visit per month 	
--	---	--

	
 o G0316, G0319, ESRD related services during the course of treatment, for patients 12-19 and 20 yrs of age and over to include monitoring for the adequacy of nutrition, etc. w/1 physician visit per month o G0322, G0323, ESRD related services for home dialysis patients per full month: for patients 12-19 and 20 yrs of age and over to include monitoring for adequacy of nutrition and etc. o G0326, G0327, ESRD related services for home dialysis (less than full month), per day; for patients 12-19 and 20 yrs of age and over o S9335, Home therapy, hemodialysis; administrative services, professional pharmacy services, care coordination, and all necessary supplies and equipment (drugs and nursing services coded separately), per diem o S9339, Home therapy, peritoneal dialysis, administrative services, care coordination and all necessary supplies and equipment, per diem 
OR
 
Kidney transplant, defined as either 1 inpatient or 1 outpatient code Codes include:
 
 - ICD9 prox codes: 
 o 55.6x, Transplant of kidney (Exclude 55.61) - CPT4 codes: 
 o 50360, Renal allotransplantation, implantation, graft, w/o donor & recipient nephrectomy o 50365, Renal allotransplantation, implantation, graft, w/ donor & recipient nephrectomy 	
--	---	--

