	The primary outcome is the time to the first occurrence of CV death, non-fatal myocardial infarction (MI) or non-fatal stroke—the so-called 3-point major adverse CV events (3P-MACE) composite outcome.	
Measured 1 days after drug initiation in diagnosis position specified below and inpatient care setting:
 
Inpatient mortality/MI/Stroke –
 
For MI Any diagnosis position in inpatient care setting ICD-9 Dx 410.X (acute myocardial infarction) excluding 410.x2 (subsequent episode of care)
 
For stroke Primary diagnosis position in inpatient care setting ICD-9 discharge diagnosis: 430.xx Subarachnoid hemorrhage (SAH) 431.xx Intracerebral hemorrhage (ICH) 433.x1 Occlusion and stenosis of precerebral arteries with cerebral infarction 434.xx (excluding 434.x0) Occlusion and stenosis of cerebral arteries with cerebral infarction 436.x Acute, but ill-defined cerebrovascular events
 
Mortality- See Mortality Sheet.
	
For MI:
 
►PPV 94% in Medicare claims data [Kiyota Y, Schneeweiss S, Glynn RJ, Cannuscio CC, Avorn J, Solomon DH. Accuracy of Medicare claims-based diagnosis of acute myocardial infarction: estimating positive predictive value on the basis of review of hospital records. American heart journal 2004;148:99-104.]
 
►PPV 88.4% in commercially-insured population [Wahl PM, Rodgers K, Schneeweiss S, et al. Validation of claims-based diagnostic and procedure codes for cardiovascular and gastrointestinal serious adverse events in a commercially-insured population. Pharmacoepidemiology and Drug Safety 2010;19:596-603.]
 
For stroke:
 
PPV of 85% or higher for ischemic stroke PPV ranging from 80% to 98% for hemorrhagic stroke
 
 
 
	Can't be measured in claims but not important for the analysis
	INCLUSION CRITERIA			

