Appendix A

Mortality- Dependent on data source.

1. All-cause mortality / inpatient mortality

Identified using the vital status file-

Medicare

Identified using the discharge status codes-

Optum-

- 20 = EXPIRED
- 21 = EXPIRED TO BE DEFINED AT STATE LEVEL
- 22 = EXPIRED TO BE DEFINED AT STATE LEVEL
- 23 = EXPIRED TO BE DEFINED AT STATE LEVEL
- 24 = EXPIRED TO BE DEFINED AT STATE LEVEL
- 25 = EXPIRED TO BE DEFINED AT STATE LEVEL
- 26 = EXPIRED TO BE DEFINED AT STATE LEVEL
- 27 = EXPIRED TO BE DEFINED AT STATE LEVEL
- 28 = EXPIRED TO BE DEFINED AT STATE LEVEL
- 29 = EXPIRED TO BE DEFINED AT STATE LEVEL
- 40 = EXPIRED AT HOME (HOSPICE)
- 41 = EXPIRED IN A MEDICAL FACILITY (HOSPICE)
- 42 = EXPIRED - PLACE UNKNOWN (HOSPICE)

Truven-

- 20 - Died
- 22 - Died
- 23 - Died
- 24 - Died
- 25 - Died
- 26 - Died
- 27 - Died
- 28 - Died
- 29 - Died
- 40 - Other died status or Expired at home (Hospice claims only) (depends on year)
- 41 - Other died status or Expired in medical facility (Hospice claims only) (depends on year)

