Appendix A

- 42 - Other died status or Expired - place unknown (Hospice claims only) (depends on year)
- 21 - Died or Disch./Transf. to court/law enforcement (depends on year)

2. CV mortality

Information on CV mortality through data linkage with the National Death Index (NDI) will be available for Medicare at a later date. We will conduct secondary analyses using CV mortality at that time.

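### The primary endpoint is named with CV death but built with death from any cause, which can bias the 1.3 non-inferiority test toward success; add a pooled MI-or-stroke sensitivity analysis and relabel the endpoint

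*Combined protocol and SAP*

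**What the plan says.** Section 1.2 sets the hypothesis that linagliptin is "non-inferior with a hazard ratio of < 1.3 compared with placebo as assessed by the time to first occurrence" of a 3P-MACE event. Section 6.3.1 names the primary outcome as "non-fatal myocardial infarction, non-fatal stroke, or CV mortality".

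The construction differs from the name. The primary-outcome row of Appendix A builds the endpoint as "Inpatient mortality/MI/Stroke", with no cause-of-death filter, and refers to the Mortality sheet for the death component. That sheet uses discharge status codes for Optum and MarketScan (listed there as Truven). For Medicare it says "Identified using the vital status file", under a heading that covers all-cause and inpatient mortality. Section 6.3.1 states openly, for the commercial databases, that "All-cause inpatient mortality identified using discharge status codes will be used as a proxy" for CV mortality.

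CV death from the National Death Index (NDI) "will only become available at a later date for Medicare and will be used in secondary analyses". The Mortality sheet repeats this: "We will conduct secondary analyses using CV mortality at that time".

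The secondary outcomes are hospitalised MI, hospitalised stroke (each including fatal cases) and mortality, each analysed separately. Section 13.1 gives a Cox HR for each outcome, section 13.2 adds a trimmed, PS-decile-adjusted analysis, and section 14.1 reports each endpoint with a 95% CI. No combined MI-or-stroke outcome is listed, and the plan does not discuss how the death proxy affects the comparison with 1.3.

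**The concern.** A composite HR is roughly an event-weighted average of its component HRs. If some counted events are deaths that the drug does not influence, they contribute an HR of 1 and pull the composite toward 1. In a superiority test this costs power. In a non-inferiority test it can favour a positive conclusion, because a harmful HR at the margin appears smaller than it is. A large sample does not protect against this; it estimates the diluted HR more precisely.

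Applying one death rule in all databases would not remove the problem. It arises because cause of death is unavailable for the primary analysis in all three. At stake is whether an upper limit below 1.3 can be reported as non-inferiority for CV death, MI or stroke, or only for MI, stroke or death from any cause.

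**Working it through.** **Inputs**
- Margin 1.3, assumed HR 1, two-sided alpha 0.05 (sections 1.4 and 10).
- Expected events: Optum 293.928, MarketScan 325.9784, Medicare 2,830.11586; stated pooled figure 2,638.4153 (section 10).
- Deaths ending follow-up in the matched cohort under the dummy outcome: 1,704 of 101,830, being 929 referent and 775 exposed (section 9).
- Not in the documents: the non-CV share of deaths and the HR for non-CV death. Both are assumed below and varied.

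**Reproducing the plan's power.** Power = Phi(ln 1.3 × √D / 2 − 1.96). With D = 2,638.4 this gives 0.999999116, as stated. The same formula reproduces Optum (0.6137), MarketScan (0.6586) and Medicare (0.99999974).

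**Which event total.** The database tables sum to 293.9 + 326.0 + 2,830.1 = 3,450.0. The stated pooled 2,638.4 uses 25.91 per 1,000, the unweighted mean of 16.55, 18.7 and 42.47; the size-weighted risk is 33.88. Since 2,638 is below Medicare alone, 3,450 is the better total. Medicare supplies 2,830.1/3,450.0 = 82% of it.

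**Death share.** 1,704/3,450.0 = 49.4% (on the stated pooled count, 1,704/2,638.4 = 64.6%). This is a ceiling, because a death after an on-study MI or stroke is not a first event. It also counts genuine CV deaths.

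**Dilution.** Let q = death share × non-CV share of deaths, and let the true HR on the CV components be 1.3. With non-CV death HR 1, composite HR = 1.3(1 − q) + q, and P(declare non-inferiority) = Phi[(ln 1.3 − ln HR) × √3,450 / 2 − 1.96].
- Deaths 35%, non-CV 30%: q = 0.105, HR = 1.27, probability 10.8%.
- Deaths 49.4%, non-CV 60%: q = 0.296, HR = 1.21, probability 54.8%.
- With 2,638 events and the same shares, the range is about 9-44%.
- With deaths only 20% of first events (3,450 events), it is about 6-13%.

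**Varying the non-CV death HR** (deaths 49.4% of 3,450 events, true CV HR 1.3):

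| Non-CV death HR | 25% of deaths non-CV | 50% of deaths non-CV |
|---|---|---|
| 0.83 | 26% | 78% |
| 1.0 | 13% | 41% |
| 1.3 | 2.5% | 2.5% |
| 1.5 | 0.6% | 0.1% |

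These treat q as a reference-arm share. Treating it as a share of events in both arms gives somewhat higher values below 1.3 (for example 48% instead of 41%).

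**MI-or-stroke composite, removing all 1,704 deaths.** 3,450 − 1,704 = 1,746 events: power Phi(ln 1.3 × √1,746 / 2 − 1.96) = 0.9998, SE of log HR 2/√1,746 = 0.048. From the stated pooled count: 934 events, power 0.98, SE 0.065. The full composite has SE 2/√3,450 = 0.034.

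**The case against.** The proxy is disclosed, and the plan has partial safeguards. MI and stroke are each analysed with fatal cases but without unrelated deaths, and reported with 95% CIs. NDI-based CV mortality is promised for Medicare, which carries most of the events. A CV effect near 1.3 should leave some trace in those results. This stands, so it would be wrong to infer that the plan has no guard. The gap is narrower: no analysis combines the two CV events that are directly measured, each alone has fewer events than the two together, and NDI data are undated and absent for the commercial databases.

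A reader might also infer that the proxy necessarily pulls the HR toward 1 and makes the test anti-conservative. The documents do not support that. It needs a CV HR above 1 and a non-CV death HR closer to 1 or below it, and neither is given. In a non-randomised comparison, non-CV death may be confounded in either direction. The raw death counts do not settle it: 775/929 = 0.83, but exposed follow-up is shorter, and scaling by the Medicare medians (148/127 days) gives about 0.97, for deaths of all causes. At the plan's assumed HR of 1.0 with null non-CV deaths there is no dilution. At the trial's 1.02 the shift is at most 0.02 × 0.296, about 0.006.

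Nor does 49% mean that half the primary events are misclassified. It is a ceiling on deaths of every cause, taken from a censoring table rather than from primary-endpoint events.

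**Conclusion.** The mismatch between the named and constructed endpoint is clear from the text and applies in all three databases. Its effect on the non-inferiority test is conditional. With a true CV HR of 1.3, non-CV death HR 1, deaths 35-49% of first events and 30-60% of deaths non-CV, false non-inferiority is about 11-55% against a nominal 2.5%. Inflation vanishes when the non-CV death HR is also 1.3 and reverses above that. Because that HR and the non-CV share are unknown, the direction cannot be settled from the documents, which is the reason for a planned check free of non-CV deaths.

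A reader might go further and require both the primary and an MI-or-stroke upper limit to fall below 1.3. That would be a co-primary rule. Sections 13 and 14 set no such decision rule, and MI-or-stroke is not the endpoint being replicated, so the evidence supports a sensitivity analysis only. The point is a worthwhile, inexpensive improvement, not a fatal flaw.

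**What to change.** 1. In sections 6.3.1 and 13.1, add time to first hospitalisation for MI or stroke (fatal cases included, Appendix A codes) as a pre-specified sensitivity analysis in the same matched cohort. Report its HR and 95% CI beside the 1.3 margin.
2. Label the current primary endpoint, and any conclusion drawn from it, as MI, stroke or all-cause death until NDI data arrive.
3. Reconcile the primary-outcome row of Appendix A, which speaks of inpatient mortality, with the Mortality sheet, which uses the vital status file for Medicare, and state whether out-of-hospital Medicare deaths count.

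The cost is one extra Cox model on variables already built. The estimate is less precise than the primary (SE as shown above) but keeps power of at least 0.98 in the pooled data on either event count. It omits CV deaths without an MI or stroke admission, so it supports the primary analysis and does not replace it.
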